6.2 Exclusion Criteria (All Participants)

An individual who meets any of the following criteria will be excluded from participation in this study:

1. Below average estimated premorbid cognitive functioning (based on WRAT-4 reading recognition standard z-score < 85).
2. Presence of severe cognitive impairment (based on SDMT age normative z-score <-3.0).
3. Primary psychiatric disorder that would influence ability to participate.
4. Current uncontrolled seizure disorder.
5. Current substance abuse disorder.
6. History of head trauma in the past year (e.g., head injury, brain surgery) or medical device implanted in the head (such as Deep Brain Stimulator) or in the neck (such as a Vagus Nerve Stimulator).
7. Pregnant or breastfeeding

6.2.1 Additional Exclusion Criteria for tDCS-MRI Participants

1. Extreme claustrophobia
2. Any skin disorder/sensitive skin (e.g., eczema, severe rashes), blisters, open wounds, burn including sunburns, cuts or irritation, or other skin defects which compromise the integrity of the skin at or near stimulation locations (where electrodes are placed)
3. Treatment for a communicable skin disorder currently or over the past 12 months
4. Have any irremovable piercings, metallic based-tattoos, or MRI-contraindicated implants (e.g. pacemakers and defibrillators)

6.3 Vulnerable Subjects

N/A. Vulnerable subjects will not be recruited for this study.

6.4 Strategies for Recruitment and Retention

Research participants will be recruited from the NYU Langone Health MS Comprehensive Care Center (MSCCC) patient database. Additionally, an IRB approved study description will be posted on the website of the National Multiple Sclerosis Society and shared with the appropriate list-service. Moreover, IRB approved flyers will be posted in the clinic of the MS Comprehensive Care Center. Interested participants who learned of the study through word of mouth may reach out directly to the research team members. Patients who are seen by medical staff at NYU Langone Health, who fit eligibility criteria, will be referred by the study PI and sub-investigators. All recruiting division neurologists and medical staff will be presented with the study description. A patient who is seeing one of these medical staff members as their treating physician will be introduced to the study by that medical staff member. If the patient is interested and agrees, then a member of the research study staff will contact them. An IRB-approved phone script will be used to inform the patient about the study and to ask eligibility questions. Verbal responses will be recorded on a separate pre-screen verbal checklist.

CONFIDENTIAL

This material is the property of the NYU Langone. Do not disclose or use except as authorized in writing by the study sponsor
Observational Study Template Version: 8 February 2019

If a potential subject is ineligible or does not provide written consent the information collected including all PHI collected for the purposes of this study will be destroyed immediately.

6.4.1 Use of Epic Information for Recruitment Purposes

N/A

6.5 Duration of Study Participation

Study participation involves 1 visit that will last approximately 1.5-3.5 hours. The study visit will include:

- Consent (~25 minutes),
- Eligibility clearance by study clinician (e.g. Neurologist or Nurse Practitioner), eligibility can be confirmed either over the phone, research video visit, or review of medical record from an external provider (30 minutes)
- Cognitive assessment (30 minutes)
- Optional gait assessment (20 minutes)
- **[MRI-tDCS group only]** tDCS tolerability test (2 min)
- ***[MRI-tDCS group only]** MRI scan with simultaneous tDCS (60 minute scan plus an additional 40 minutes to walk to CBI, change clothes, complete MRI safety form, etc.).

**Participants in the MRI-tDCS group may opt to complete the scan on a separate visit.*

6.6 Total Number of Participants and Sites

This study will recruit a total of 60 participants (target for participants who complete the tDCS-MRI is n=30 and target for participants who complete the cognitive assessment only is n=20 for total target of n=50, plus 10 to account for screen fails and withdrawals) at NYU Langone Health.

6.7 Participant Withdrawal or Termination

6.7.1 Reasons for Withdrawal or Termination

Participation in the study is voluntary and participants are free to withdraw from the study at any time upon request. An investigator may terminate participation in the study if:

- Any clinical adverse event (AE), laboratory abnormality, or other medical condition or situation occurs such that continued participation in the study would not be in the best interest of the participant.
- The participant meets an exclusion criterion (either newly developed or not previously recognized) that precludes further study participation.

6.7.2 Handling of Participant Withdrawals or Termination

If a participant wishes to withdraw from the study, they may do so at any point without adversely effecting any standard-of-care treatment. Participants will be provided with study team e-mail and contact number and can withdraw at any time.

Data of participants who withdraw or are terminated from the study may be kept for analysis if the data is usable (as determined PI).

6.7.3 Premature Termination or Suspension of Study

This study may be temporarily suspended or prematurely terminated if there is sufficient reasonable cause. If the study is prematurely terminated or suspended, the PI will promptly inform the IRB and will provide the reason(s) for the termination or suspension.

Circumstances that may warrant termination or suspension include, but are not limited to:

- Determination of unexpected, significant, or unacceptable risk to participants.

CONFIDENTIAL

This material is the property of the NYU Langone. Do not disclose or use except as authorized in writing by the study sponsor
Observational Study Template Version: 8 February 2019

- Demonstration of inefficacy that would warrant stopping
- Data that are not sufficiently complete and/or evaluable

Study may resume once concerns about safety, protocol compliance, data quality are addressed and satisfy the IRB.

7 Study Schedule

7.1 Eligibility Pre-screening

- Eligibility pre-screen to determine general eligibility.
- Obtain medical records.

7.2 Study Visit

- Obtain written informed consent (approximately 25 minutes or however much time is needed)
- Study clinician confirms patient's diagnostic eligibility based on inclusion/exclusion criteria in-person at the research visit. Alternatively, this can be done via phone, Zoom or Webex, prior to the baseline visit. Patients seen clinically at the NYU MSCCC may have their diagnostic eligibility confirmed without speaking to the study clinician prior to the baseline visit.
- Complete self-reported questionnaire-- Patient Determined Disease Steps²⁶ (PDDS, 5 minutes)
- Complete cognitive assessment (Cogstate and BICAMS, 30 minutes)
- Complete self-report questionnaire (paper form) (15 minutes).
- (Optional for all participants) Gait assessment (approximately 20 minutes)
- [tDCS-MRI group only] Perform tDCS tolerability test (2 minutes)
- [tDCS-MRI group only] Complete tDCS-MRI scan (40 minutes to prepare for scan, change, etc. and 60 minutes for scan [including 20-minutes of tDCS]).

8 Study Procedures

8.1 Baseline Procedures

After the participant provides written informed consent, the following research procedures will take place:

8.1.1 All Participants

- A study clinician will meet with the participant to confirm their eligibility according to the MS or prodromal MS inclusion criteria. Depending on patient and clinician availability, the clinician can either meet the patient in-person on the day of the research visit in a private room at NYU MSCC ([name], or [name]). Alternatively, the clinician can speak to the patient via phone, Zoom, or Webex prior to the baseline visit to confirm eligibility. Patients who are known to the NYU MSCCC can have their eligibility confirmed by a study clinician without meeting with the patient. Patients who have been diagnosed with MS less than five years and who receive their care from an external provider can provide their medical record or a letter from their neurologist indicating the date and nature of their MS diagnoses to confirm eligibility.
- Participants will complete a cognitive assessment (measures described in section 8.2).
- Optional gait assessment: Participants will have the option to complete a brief gait assessment administered by a trained study team member. Participants will be asked to walk at their self-selected speed back and forth for 2 minutes along a 30 meter hallway ([name], or [name]) in order to collect at least 30 steps to calculate the motor IIV. The gait assessment will be

CONFIDENTIAL

This material is the property of the NYU Langone. Do not disclose or use except as authorized in writing by the study sponsor
Observational Study Template Version: 8 February 2019

repeated twice. During one walking task, participants will wear an inertial sensor around their waist (G-Sensor, BTS Bioengineering), while during the other will wear the inertial sensor on their shoe (Runscribe). The inertial sensor used will depend on availability. Both devices connect to a study iPad via Bluetooth and obtain data such as walking speed, balance, and stride length, etc. Identifying information will not be saved to the iPad or the sensors.

8.1.2 MRI-tDCS group only

- **tDCS tolerability test:** In a private room at CBI, a study team member will place the tDCS headset on the participant (dorsolateral prefrontal cortex montage, left anodal) and administer a 60-second tDCS stimulation test, with a 30-second ramp up to target 2.0mA, followed by a 30-second ramp down. Participants who cannot tolerate 2.0mA will be excluded from the study.
- **MRI scan with simultaneous tDCS:** At CBI, participants will be asked to complete an MRI Safety Questionnaire per standard protocol for radiology procedures. Participants who cannot confirm their pregnancy status will be given a urine pregnancy test and may only continue in the study if the test is negative. Participants will be asked to change into an MRI compatible patient robe in a private room and place their belongings in a locker for safe keeping.

Next, they will be taken to the MRI suite and asked to lie down on the MRI table. A team member will place the MRI-compatible tDCS headset on the participant's head). Participants will be given a squeeze ball which can be used to alert the MRI technicians at any time during the scan should they need assistance. Participants will also be monitored by a study team member for the entirety of the MRI-tDCS scan. The set-up of the device and administration of stimulation will be done by an onsite study team member.

The tDCS-MRI scan will last approximately one hour. The first 20 minutes of the MRI will not include tDCS stimulation. After 20 minutes, the tDCS device will ramp up to 2.0mA and deliver 2.0mA for 20 minutes. Then the tDCS will ramp down (30 seconds) and the final 20 minutes will be without stimulation. At the conclusion of the MRI, the participant will be paid for their participation.

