3.1.1 Known Potential Risks

Risks associated with cognitive assessments and questionnaires: Completing questionnaires may produce some emotional distress in some participants. While we don't anticipate this will be a significant issue, participants will be allowed to take breaks as needed and may stop answering questions at any time without affecting their enrollment.

Risks associated with tDCS: There are no major risks associated with tDCS. Some people report head tingling, itchiness at the site of anodal stimulation, and a mild heating sensation. These irritations are usually mild and tolerable.

As in our previous MRI-tDCS study, we will use a Soterix Medical tDCS device (<https://soterixmedical.com/research/1x1/tdc>) to administer ~20 minutes of stimulation during the MRI scan. The Soterix 1x1 tDCS device is outside of the MRI suite in the MRI control area. The cables used to connect the tDCS device to the tDCS headset/electrodes (which will be inside the MRI suite) are MRI-certified carbon cables. In addition, between the MRI control room and the MRI suite is a patch panel with an MRI filter. So far, no tDCS sessions delivered during the MRI scan were aborted due to safety or tolerability concerns. The most commonly reported side effects were skin tingling, sensations of warmth, and skin itching.

For the reasons referenced above, tDCS meets the criteria for an abbreviated IDE (non-significant risk medical device):

1. It is **not** intended as an implant and **does not** present a potential for serious risk to the health, safety, or welfare of a subject
2. It is **not** purported or represented to be for a use in supporting or sustaining human life and **does not** present a potential for serious risk to the health, safety, or welfare of a subject.
3. It is **not** for a use of substantial importance in diagnosing, curing, mitigating, or treating disease, or otherwise preventing impairment of human health and **does not** present a potential for serious risk to the health, safety, or welfare of a subject: the device will not be used for subject treatment and subjects standard medical treatment will continue regardless of their participation in the study
4. It **does not** otherwise present a potential for serious risk to the health, safety, or welfare of a subject²³⁻²⁵.

CONFIDENTIAL

This material is the property of the NYU Langone. Do not disclose or use except as authorized in writing by the study sponsor

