3.1.1.1 Other risks

There is minimal risk of breach of confidentiality. All data will be obtained on paper CRF and kept strictly confidential and stored in locked cabinets located at [name]. Participants will be assigned a unique ID that will be used on all data collection instruments. The identifying link will be stored in a separate file and saved on password-protected NYU servers.

Unforeseeable Risks: While not expected, there may be risks associated with tDCS that are not known at this time.

CONFIDENTIAL

This material is the property of the NYU Langone. Do not disclose or use except as authorized in writing by the study sponsor
Observational Study Template Version: 8 February 2019

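### Section 8.1.2 lists the tDCS tolerability test ahead of the only named pregnancy check, so a participant with unconfirmed status could receive current first

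*Combined protocol and SAP*

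**What the plan says.** Section 6.2, item 7, lists "Pregnant or breastfeeding" among the exclusions for all participants. It gives no method or time for the check.

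Section 8.1.2 describes the MRI-tDCS group's procedures at the imaging center (CBI) in two bullets. In the first, a team member fits the headset and will "administer a 60-second tDCS stimulation test, with a 30-second ramp up to target 2.0mA", followed by a ramp down. The second covers the scan. It begins with the MRI Safety Questionnaire and then gives the pregnancy provision: "Participants who cannot confirm their pregnancy status will be given a urine pregnancy test and may only continue in the study if the test is" (a negative result is required). The scan itself delivers 2.0 mA for 20 minutes. "Then the tDCS will ramp down (30 seconds"), and the last 20 minutes are without current.

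Section 9.6.4 says that a positive test leads to exclusion, without any timing. Section 8.4, on laboratory procedures, is marked not applicable.

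On risk, section 3.1.1 states that "tDCS meets the criteria for an abbreviated IDE (non-significant risk medical device"). Section 3.1.1.1 adds that "there may be risks associated with tDCS that are not known at this time".

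**The concern.** An exclusion criterion protects a participant only if it is checked before the exposure it is meant to prevent. Here the first current comes in the tolerability test, and the only pregnancy check that the procedures name is in the step listed after it. The check exists because the protocol expects some participants to arrive at CBI unable to confirm their status. Those are the people who could be stimulated first.

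What is at stake is a short, avoidable exposure in people the study means to exclude. The protocol accepts that tDCS may carry unknown risks, so it is sensible for its own check to come before any current. The point concerns this one step in the MRI-tDCS group. It does not address how the exclusion is checked in the cognitive-only group.

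**Working it through.** **Order of steps.** The sections that bear on the order say the following.

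- Section 6.4 (recruitment): "An IRB-approved phone script will be used to inform the patient about the study and to ask eligibility questions". The script is not in the documents, and pregnancy is not named.
- Section 7.1: a pre-screen for general eligibility. Pregnancy is not named.
- Section 7.2: a clinician confirms diagnostic eligibility against the inclusion and exclusion criteria. No pregnancy question or test is named. Patients of the MS center may be confirmed without speaking to the clinician.
- Section 8.1.2, first bullet: tolerability test, with current up to 2.0 mA.
- Section 8.1.2, second bullet: MRI Safety Questionnaire, conditional urine test, then the scan.
- Section 13.3.1: consent must be signed before any study procedure. The protocol therefore states a required order where it wants one. It states none between the pregnancy check and the first stimulation.

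Sections 6.5 and 7.2 also list the tolerability test before a 40-minute preparation block, but neither names a pregnancy check. They are not used here as proof of order.

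**Size of the exposure.** The plan gives no charge figure to reproduce. The inputs are the 2.0 mA target, the 60-second test, its 30-second ramps, the 20-minute scan stimulation and the scan's 30-second ramp down (all section 8.1.2), and the 2 minutes allotted to the test (sections 6.5 and 7.2). Ramps are assumed linear. Charge is current × time, and a linear ramp delivers half of that.

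- One ramp: 0.5 × 2.0 mA × 30 s = 30 mC.
- Reading A, where the 60 seconds are the two ramps only: 2 × 30 = 60 mC.
- Reading B, where 60 seconds at 2.0 mA are added to both ramps (120 s in all, matching the 2 minutes allotted): 2.0 × 60 + 60 = 180 mC.
- Scan plateau: 2.0 × 20 × 60 = 2,400 mC.
- Share of plateau: 60 / 2,400 = 2.5% (A); 180 / 2,400 = 7.5% (B).
- Scan including ramps, with the ramp up assumed to be 30 s as well: 2,400 + 30 + 30 = 2,460 mC. The shares become 60 / 2,460 = 2.4% and 180 / 2,460 = 7.3%.
- Share of time: 60 / 1,200 = 5% (A); 120 / 1,200 = 10% (B).

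The peak is 2.0 mA in both the test and the scan. The documents give no relation between dose and risk, so these figures show only that the exposure is small.

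**Number affected.** Eligible ages are 21 to 59 (section 6.1). The documents give no sex split and no share with unconfirmed status, so no count is estimated.

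**The case against.** The strongest reply is that list order in this protocol is not time order. Section 6.5 lists the tolerability test before a block that includes the walk to CBI, yet section 8.1.2 holds the test at CBI. Part of the block listed second may therefore happen first, and the MRI safety form is in that block. Within section 8.1.2, explicit time words mark sequence during the scan, but none links the two bullets. This stands: the order is one of listing, and staff could check first. What remains is that no sentence requires them to.

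A second reply is that the phone script, the pre-screen and the clinician review may already settle pregnancy status, and that the script, the MRI questionnaire or a manual of procedures may fix the order. This too has weight, and it may cover most people. But none of those steps is stated to cover pregnancy, and section 8.1.2 still provides for participants who cannot confirm their status.

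Third, the urine test sits beside the radiology questionnaire and can be read as a condition for the MRI alone. The wording goes further: it makes continuing in the study, not only the scan, depend on a negative test.

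Fourth, section 6.7.1 lets the investigator end participation for an exclusion "either newly developed or not previously recognized". That power acts after recognition, so it does not put the check before the first current.

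Finally, the safety rationale is modest. The device is classed as non-significant risk, and the only support for caution is a general sentence on unknown risks. That is a fair reason to keep the point at the lowest severity.

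**Conclusion.** The point holds as a minor safety sequencing gap. Followed as listed, section 8.1.2 would allow a participant with unconfirmed pregnancy status to receive 60 to 120 seconds of stimulation, peaking at 2.0 mA, before the study's own exclusion is checked. The conclusion assumes that staff follow the listed order and that earlier screening has left the participant's status open. Neither is certain, and the number affected may be zero.

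No harm is shown. The point is worth raising because the correction is nearly free and takes the exposure before the check to zero.

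**What to change.** In section 8.1.2, make the MRI Safety Questionnaire and the pregnancy-status check, with the existing conditional urine test, the first step at CBI. State that no stimulation, including the tolerability test, is given until both are clear. List the same order in sections 6.5 and 7.2.

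For participants who have the scan on a separate visit, the protocol does not say on which day the tolerability test is held. Either hold it on the scan visit, after the check, or keep it on the first visit with a check before it and repeat the check before the scan.

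On a single visit this adds no procedure. With separate visits, repeating the check costs one further questionnaire, and a further urine test only if status is unconfirmed. Holding the tolerability test on the scan visit avoids the repeat, but intolerance of 2.0 mA is then found only on the scan day.

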8.2 Cognitive Assessments

- **Wide Range Achievement Test- 4th Edition (WRAT-4)** Reading Recognition Subset: The WRAT-4 is a brief test of single word reading recognition that provides a proxy of literacy and general intellectual ability.
- **Symbol Digit Modalities Test (SDMT)**: The SDMT is 90-second cognitive task in which the participant is shown a sheet containing rows of symbols. Each symbol corresponds to a specific number. The participant's task is to say out loud the number associated with each symbol. The SDMT is used as a general cognitive screen to detect severe cognitive impairment.
- **Brief International Cognitive Assessment for MS (BICAMS)**: this battery tests mental processing speed and memory. BICAMS includes the following tests: Brief Visuospatial Memory Test (BVMT, requires the participant to look at a sheet with 6 shapes on it for 10 seconds and then draw as many shapes as they can from memory); the Rey Auditory Verbal Learning Test (RAVLT, requires the participant to recite back a list of words from memory as best they can), and SDMT described above.
- **Cogstate Brief Battery (CBB)**: The core Cogstate RT tasks involve a deck of cards on a green background screen and the participant answers "yes" or "no" by hitting a keyboard key ("D" or "K") across repeated trials. Each task first includes instructions and practice period before the test begins

CONFIDENTIAL

This material is the property of the NYU Langone. Do not disclose or use except as authorized in writing by the study sponsor
Observational Study Template Version: 8 February 2019

and takes approximately 3-4 minutes to complete (for a total of ~7 minutes). The representative timed RT scores are provided by the Detection task (indicating when a card is revealed; DET/simple RT), Identification task (“is the card revealed black or red?”, IDN/choice RT), and One-Back (“Is this the card that you just saw?”). Performance is characterized by near complete accuracy (i.e. all, or almost all, items are answered correctly), and validity checks are built into the scoring. The primary IIV outcome measure is calculated as intraindividual standardized deviations (ISD) in RTs across both tasks, measured in milliseconds and with log10 transformation.

[figure not shown]
